14.1.2 Primary Objectives for Phase II Trial

After MTD is established in Phase I, 20 additional patients will be enrolled in the Phase II study and treated with pyrimethamine at the MTD. The primary objective for this portion of the study is to determine the overall response rate of pyrimethamine in these patients, including both CLL/SLL and T-LGL.

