14.2.2 Phase II

The Phase II portion is a single arm study which consists of determining the overall response rate of pyrimethamine in relapsed CLL/SLL and T-LGL patients. The overall response rate is not expected to differ between these two diseases and therefore one overall response rate will be reported. A 35% overall response rate will be considered promising. The first response evaluation will be assessed after the first cycle of treatment then at the end of three cycles.

Six Phase I patients treated at the MTD of pyrimethamine will be enrolled in the Phase II part of the study. A Simon's two stage optimal design is used to compute the sample size. A total number of 26 patients is needed in order to detect a 35% response rate, assuming the ORR for the null hypothesis is 10%, with 90% power and 10% type I error. The study will stop early if only 1 or 0 responses out of the first 10 patients is observed, and the drug will not be declared promising if less than 5 responses are seen in the total 26 patients. The probability of stopping at the first stage if the true ORR is less than 35% is 0.736.

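### Section 14.2.2 gives 0.736 as the stage 1 stopping probability for any true ORR below 35%, but the figure holds only at the 10% null

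*Combined protocol and SAP*

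**What the plan says.** Section 14.2.2 sets out a single-arm, two-stage Phase II design:

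- **Rates.** The null ORR is 10%. The alternative is given by "A 35% overall response rate will be considered promising".
- **Error limits.** The design is sized "with 90% power and 10% type I error".
- **Stage 1 rule.** "The study will stop early if only 1 or 0 responses out of the first 10 patients is observed".
- **Final rule.** "the drug will not be declared promising if less than 5 responses are seen in the total 26 patients".
- **Design label.** "A Simon's two stage optimal design is used to compute the sample size", and 26 patients are said to be needed.
- **Performance of the stage 1 look.** "The probability of stopping at the first stage if the true ORR is less than 35% is 0.736".

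The 26 patients are six carried over from Phase I at the MTD plus those in section 14.1.2, where "20 additional patients will be enrolled in the Phase II study". No other section restates or qualifies the stopping probability.

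**The concern.** The chance of seeing at most one response in 10 patients depends on the true response rate, so one number cannot describe every rate below 35%. The sentence also sets its boundary at the alternative, whereas a stage 1 stopping probability is normally quoted at the null.

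This is the only figure the plan gives for the futility look. Taken at its word, it tells an IRB, the DSMC or an investigator that a drug falling short of the 35% target is halted after 10 patients about three times in four. If that is untrue for drugs of middling activity, the plan overstates how far stage 1 limits exposure to them.

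Checking the design raises a second, smaller question: whether 10 then 26 patients is what Simon's optimal criterion gives for the stated inputs.

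**Working it through.** **Inputs, all from section 14.2.2.** Null rate 0.10; alternative 0.35; type I error at most 0.10; power at least 0.90; stop at 0 or 1 of 10; not promising at 4 or fewer of 26. Stage 2 therefore adds 26 − 10 = 16 patients.

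**Step 1: reproduce the plan's figure.** With true rate p, the probability of stopping at stage 1 is

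PET(p) = (1 − p)^10 + 10 p (1 − p)^9.

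At p = 0.10 this is 0.3487 + 0.3874 = 0.7361. The stated 0.736 is correct at the null.

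**Step 2: apply the formula across the range the sentence names.** Expected total N is 10 + 16 × (1 − PET). The plan states no expected N; it is derived here to show scale.

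| True ORR | PET | Probability of going on | Expected total N |
|---|---|---|---|
| 5% | 0.914 | 0.086 | 11.4 |
| 10% | 0.736 | 0.264 | 14.2 |
| 15% | 0.544 | 0.456 | 17.3 |
| 20% | 0.376 | 0.624 | 20.0 |
| 25% | 0.244 | 0.756 | 22.1 |
| 30% | 0.149 | 0.851 | 23.6 |
| 34% | 0.096 | 0.904 | 24.5 |
| 35% | 0.086 | 0.914 | 24.6 |

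PET falls strictly as p rises, so it equals 0.736 at 10% and nowhere else. Reading the sentence as a bound does not save it: as a lower bound it fails for every rate above 10%, and as an upper bound it fails for every rate below 10%.

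The expected N counts the six Phase I patients. Expected new enrolment is six fewer on each line: 8.2 at 10%, 14.0 at 20% and 17.6 at 30%.

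**Step 3: check that the rule meets the stated limits.** The drug is declared promising with probability

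Σ (x = 2 to 10) P(X1 = x) × P(X2 ≥ 5 − x), with X1 ~ Bin(10, p) and X2 ~ Bin(16, p).

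- At p = 0.10: 0.1937 × 0.2108 + 0.0574 × 0.4853 + 0.0112 × 0.8147 + 0.0016 = **0.079** (limit 0.10).
- At p = 0.35: 0.1757 × 0.9549 + 0.2522 × 0.9902 + 0.2377 × 0.9990 + 0.2485 = **0.903** (target 0.90).

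In each sum the last term covers five or more responses already seen in stage 1. Both limits are met.

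**Step 4: check the optimal label.** All two-stage designs with total N up to 35 that meet both limits were enumerated and ranked by expected N at the 10% null. Each is written as the largest failing count over the number of patients, for stage 1 and then overall.

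| Design | Type I error | Power | Expected N at null |
|---|---|---|---|
| 1/11, 3/19 | 0.099 | 0.909 | 13.42 |
| 0/8, 3/18 | 0.093 | 0.906 | 13.70 |
| 1/12, 3/18 | 0.092 | 0.908 | 14.05 |
| 1/10, 4/26 (the plan) | 0.079 | 0.903 | 14.22 |

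Simon's optimal design for these inputs is 1/11, 3/19. The plan's rule comes fourth, 14.22 − 13.42 = 0.80 patients higher. It is not the minimax design either, because 18 patients can satisfy both limits. Other inputs were tried (type I error 0.05 with power 80%, 85% or 90%; 0.10 with power 80%, 85% or 89%; and a 30% alternative with power 80% or 90%). None gave 1/10, 4/26 as its optimal or minimax design.

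**The case against.** The best case for the plan is that nothing was miscalculated. The figure 0.736 is right at the null, and the null, the alternative and the rule all stand in the same paragraph, so a statistician would see what was meant. The paragraph also limits the damage: stopping at stage 1 counts as failure, so 90% power at 35% already means that the stopping probability there cannot exceed 0.10. The plan states no expected sample size, section 14.1.2 budgets for all 20 additional patients, and no decision rests on 0.736.

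Most of this is fair, and it limits the consequence. It does not make the sentence true. The power statement shows that 0.736 cannot hold near 35%, which puts the paragraph at odds with itself, and a reader without two-stage experience has no cue to substitute 10%.

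On the label, investigators may choose a larger design than the optimal one, and this choice buys a lower type I error (0.079 against 0.099). That defends the design, but not the claim that the optimal criterion produced it.

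**Conclusion.** The sentence is wrong as written. The value 0.736 belongs to a true ORR of 10%, not to all rates below 35%. Between 10% and 35% the plan overstates early stopping by a growing margin, up to 0.736 − 0.096 = 0.64 at 34%; below 10% it understates it. At 20% to 30% the trial continues with probability 0.62 to 0.85, against the 0.264 that the text implies.

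The labels are also inaccurate: 26 patients is an acceptable size for the stated inputs, but it is neither the optimal design nor the smallest one that meets the limits. The cost is 0.8 expected patients at the null.

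These results assume independent responses with one common rate and the cut-offs applied exactly as stated. Error control and trial conduct are not affected. The fault lies in the description of the primary Phase II design and should be corrected.

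**What to change.** Replace the sentence in section 14.2.2 with wording such as: *Under this rule the trial ends after stage 1 with probability 0.736 when the true ORR is 10% and 0.086 when it is 35%.* Adding the values at 20% (0.376) and 30% (0.149) would show how the look performs in between, much as section 14.2.1 tabulates escalation probabilities by true DLT rate.

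In the same paragraph, either remove the claims that the design is optimal and that 26 patients are needed, or state the further constraint that led to 26. Reporting the attained type I error (0.079) and power (0.903) would help.

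The cost is a wording change in one section. The stage 1 rule, the final cut-off, the total of 26 and its make-up of six plus 20 patients all stay as they are.

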14.3 Primary Analysis

The overall response rate and a 90% confidence interval will also be calculated, using the method of Atkinson and Brown for a two stage study. Descriptive statistics for patients' baseline characteristics will be summarized using descriptive statistics (median, interquartile range, proportions).

14.4 Secondary Objectives

- To assess the toxicity profile of pyrimethamine in relapsed CLL/SLL and T-LGL, both acutely and over prolonged daily dosing.
- To determine pyrimethamine levels in vivo with prolonged dosing.
- To determine the progression free and overall survival following pyrimethamine for the treatment of relapsed CLL/SLL and T-LGL.
- To determine whether pyrimethamine inhibits STAT3 in vivo by assessing downregulation of STAT2 dependent gene expression in CLL cells and/or peripheral blood.
- To determine whether known prognostic factors in CLL/SLL correlate with response to pyrimethamine.
- To assess the impact of CT scans on response evaluation in relapsed CLL/SLL and T-LGL.

14.5 Secondary Analysis

Kaplan Meier method will be used to estimate the median of overall and progression free survival. The number and percent of patients who experienced toxicities on pyrimethamine after at least one dose of treatment will also be summarized. The paired t-test or Wilcoxon's signed rank test, depending on the symmetry of the data, will be used in univariate analyses for continuous variables of gene expression data, based on the ratio of post-therapy to baseline expression. Spearman's correlation coefficients will be used

for assessing relationships between continuous variables for some known prognostic factors and Fisher's exact test will be used for finding associations between categorical variables.

14.6 Reporting and Exclusions

14.6.1 Evaluation of toxicity. All participants who take at least one dose of pyrimethamine on study will be evaluable for toxicity from the time of their first treatment.

14.6.2 Evaluation of response. All participants included in the study must be assessed for response to treatment, even if there are major protocol treatment deviations or if they are ineligible. Each participant should be assigned one of the following categories: 1) complete response, 2) partial response, 3) stable disease, 4) progressive disease, 5) early death from malignant disease, 6) early death from toxicity, 7) early death because of other cause, 8) CRi or 9) unknown (not assessable, insufficient data). By arbitrary convention, category 9 usually designates the "unknown" status of any type of data in a clinical database.

All of the participants who met the eligibility criteria should be included in the main analysis of the response rate. Participants in response categories 4-9 should be considered to have a treatment failure (disease progression). Thus, an incorrect treatment schedule or drug administration does not result in exclusion from the analysis of the response rate. If a bone marrow is not assessed at restaging it will be noted on the appropriate CRF, and an otherwise complete response would become a PR.

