- be demonstrated. At a minimum, hyperuricemia, hydration, and electrolyte disturbances should be monitored closely and addressed promptly.
- 2 CT scans (chest/abdomen/pelvis) to be performed at screening in all patients and again at the end of the 1st, 3rd and 6th months of therapy; subsequent scans shall be at the discretion of the treating physician if needed for adequate response evaluation.
 - 3 Please see Section 8.3 "Determination of CLL Biologic Prognostic Factors" for details on sample collection.
 - 4 Diary dispensed with study drug and retrieved at scheduled visits.
 - 5a One heparin-anticoagulated green top tube (pharmacokinetic studies) to be collected during screening, on cycle 1 day 1 prior to drug; prior to drug on one day among days 2, 3, 4 or 5, (optional); and prior to dose (trough) at each subsequent clinic visit as per Section 8.1, above. A heparin-anticoagulated green top tube will also be collected at time of off study visit and once again 2-4 weeks later if the patient has not started additional therapy. All samples are to be delivered to the [name] lab on Mayer 5. This includes BIDMC patients.
 - 5b Two 6 cc heparinized blood for cell isolation (pharmacodynamic studies) is to be collected during screening, on cycle 1 day 1 prior to drug and approximately two hours after drug administration, prior to dose (trough) on days 2, 3 4 or 5 of therapy, pre drug on cycle 1 days 8, 15, and 22, cycle 2 days 1 and 15, and day 1 of subsequent cycles monthly up to cycle 6. Pharmacodynamic studies will also be collected at time of off study visit, 2-4 weeks later if the patient has not started additional therapy, and lastly at the 3 month follow up appointment (if subsequent therapy has not started). These are to be delivered to the [name] lab on Mayer 5. This includes BIDMC patients.
 - 6 These laboratory tests will be done at baseline, at the end of cycles 1, 3, 6, end of treatment, and every 3-6 months in follow-up.
 - 7 Bone marrow biopsy will be done at screening (unless done within previous 6 months and the Principal Investigator feels it does not need to be repeated, or if prior marrow was positive and the patient has not had CLL treatment since) and thereafter only to confirm CR. Confirmation of complete response by bone marrow biopsy should occur approximately 3 months after the clinical criteria for CR are first met. Bone marrow biopsy is not required at off study.

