10. MEASUREMENT OF EFFECT

Responses will be formally assessed initially at the conclusion of the 1st 28 day cycle, then at the conclusion of three cycles (three months), and then every three months thereafter, until disease progression, start of another treatment, or death. Response will be assessed in two ways: (1) By NCI-WG 1996 criteria³ (as updated in the IWCLL 2008 criteria Section 10.2)¹⁹ without the use of CT scans. In this case lymph nodes will be assessed based on physical exam measurements; (2) With the incorporation of CT findings as suggested for clinical trials in IWCLL 2008. Thus CT scans will be performed on all patients at the end of the 1st month, 3rd month and 6th month, if still on study we will evaluate the impact of the CT scans (1) if used only to confirm CR; (2) if used to assess lymphadenopathy regardless of PE findings. After the 6 month evaluation, further CT scans will generally not be done, but may be done at the discretion of the treating physician.

Following the initial screening bone marrow biopsy, additional bone marrow biopsies will be performed only to confirm complete remission.

T-LGL Response Criteria²¹:

Response to treatment should be evaluated by history, physical examination, and complete blood count with differential:

- Complete response — A hematologic complete response is defined as the complete normalization of blood counts (ie, hemoglobin >12 g/dL; platelets >150,000/microL; absolute neutrophil count >1500/microL; absolute lymphocyte count <4000/microL) in the setting of a circulating LGL count of less than 500/microL.
- Partial response — A hematologic partial response is defined as an improvement in blood counts that does not meet criteria for complete remission (eg, an absolute neutrophil count >500/microL or decreasing transfusion requirements).
- Treatment failure — Treatment failure is defined as an inability to achieve an at least partial response after four months of therapy.
- Progressive disease — Progressive disease is defined as a worsening of cytopenias, hepatomegaly, or splenomegaly

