10.2 Antitumor Effect – Hematologic Tumors

Parameter	CR*	PR*	PD*
Group A			
Lymphadenopathy [^]	None > 1.5 cm	Decrease ≥50%	Increase ≥50%
Hepatomegaly	None	Decrease ≥50%	Increase ≥50%
Splenomegaly	None	Decrease ≥50%	Increase ≥50%
Blood lymphocytes	<4000/μL	Decrease ≥50% from baseline	Increase ≥50% over baseline
Marrow [#]	Normocellular, < 30% lymphocytes, no B-lymphoid nodules.	≥ 30% lymphocytes, or B-lymphoid nodules, or not done	Increase of lymphocytes to more than 30% from

			normal.
	Hypocellular marrow defines CRi		
Constitutional Symptoms@	None	Any	Any
Group B			
Platelet count	> 100 000/ μ L	> 100 000/ μ L or increase \geq 50% over baseline	Decrease of \geq 50% from baseline secondary to CLL
Hemoglobin	> 11.0 g/dL (untransfused and w/o erythropoietin)	> 11 g/dL or increase \geq 50% over baseline	Decrease of > 2 g/dL from baseline secondary to CLL
Neutrophils#	> 1500/ μ L	> 1500/ μ L or > 50% improvement over baseline	Any

* CR (complete remission): all of the criteria have to be met, and patients have to lack disease-related constitutional symptoms

* PR (partial remission): at least two of the criteria of group A plus one of the criteria of group B have to be met. PR to be held at least two months and confirmed by restaging.

* SD is absence of progressive disease (PD) and failure to achieve at least a PR; PD: at least one of the above criteria of group A or group B has to be met.

^Sum of the products of multiple lymph nodes (as evaluated by CT scans in clinical trials, or by physical examination in general practice).

#These parameters are irrelevant for some response categories.

@Constitutional symptoms: Unintentional weight loss \geq 10% within the previous 6 months, significant fatigue (ECOG PS 2 or worse, Fevers >100.5F or 38.0 C for 2 or more weeks without other evidence of infection, night sweats >1 month without evidence of infection

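### The failure range in Section 14.6.2 takes in CRi, so a CLL/SLL patient whose marrow shows CRi counts as progression, while the same patient without a marrow counts as a PR

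*Combined protocol and SAP*

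**What the plan says.** Section 14.6.2 lists nine response categories. Numbers 1 to 3 are CR, PR and SD, 4 is progression, 5 to 7 are early deaths, and the list ends "8) CRi or 9) unknown (not assessable, insufficient data". The next paragraph, on the main analysis of the response rate, states: "Participants in response categories 4-9 should be considered to have a treatment failure (disease progression". It makes no exception for category 8. The same paragraph ends with a rule for a restaging marrow that was not assessed: "an otherwise complete response would become a PR".

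The CLL/SLL table in Section 10.2 puts CRi in the marrow row, with the CR criterion: "Hypocellular marrow defines CRi". For PR, the marrow entry is "≥ 30% lymphocytes, or B-lymphoid nodules, or not done", so a missing marrow is compatible with PR.

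On-study marrows are done only to confirm CR (Section 10; Study Calendar, note 7). On timing, note 7 says: "Confirmation of complete response by bone marrow biopsy should occur approximately 3 months after the clinical criteria for CR are first met".

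The T-LGL criteria in Section 10 have no marrow component and no CRi category: "Response to treatment should be evaluated by history, physical examination, and complete blood count with differential".

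**The concern.** The category list and the failure range do not fit together. Section 10.2 treats CRi as a form of complete remission, and Section 14.6.2 counts it with progression, early death and unknown. It even ranks below stable disease, which lies outside the failure range. The label also conflicts with the progression column in Section 10.2, where a hypocellular marrow is not a criterion.

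The missing-marrow rule makes this worse, because classification then depends on whether the confirmatory procedure was done. A clinical CR with no marrow is a PR and stays a responder. The same clinical CR with a hypocellular marrow becomes a failure.

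ORR is the Phase II primary endpoint and drives both Simon decisions. Section 14.2.2 refers only to numbers of responses, and ORR is never written out as a sum of categories. Section 14.6.2 is therefore the only rule that assigns CRi. A correction made after responses have been seen would be open to challenge.

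**Working it through.** **1. Category logic.** The range 4-9 is {4, 5, 6, 7, 8, 9}, and CRi is 8. Take a CLL/SLL patient who meets the clinical criteria for CR:

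| Restaging marrow | Category | Main analysis |
|---|---|---|
| Normocellular, CR criteria met | 1 (CR) | Response |
| Not done | 2 (PR) | Response |
| Hypocellular | 8 (CRi) | Treatment failure |

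Section 10.2 also requires a PR to be held for two months. A clinical CR that lasts to the marrow at about three months would normally meet that.

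**2. The plan's own design figures.** Inputs from Section 14.2.2: n1 = 10, stop at 1 or fewer responses; N = 26, not promising at 4 or fewer; null ORR 0.10; target ORR 0.35.

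- Early stop at p: P(X1 ≤ 1), with X1 ~ Bin(10, p). At p = 0.10 this is 0.3487 + 0.3874 = 0.7361, matching the stated 0.736. At p = 0.35 it is 0.0135 + 0.0725 = 0.0860.
- Declared promising at p: sum over x = 2 to 10 of P(X1 = x) × P(X2 ≥ 5 − x), with X2 ~ Bin(16, p). At p = 0.35 this is 0.9034 (stated power 90%). At p = 0.10 it is 0.0794 (stated type I error 10%).

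**3. Effect of scoring CRi as failure.** Let s be the share of all responders, CLL/SLL and T-LGL pooled, who are CRi. The document gives no value, so s is an assumption shown as a range. The true ORR including CRi is taken as 0.35, or 26 × 0.35 = 9.1 responders, so s = 10% is about one patient.

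- **(A) CRi already a failure at stage 1.** The response probability is 0.35 × (1 − s) at both stages. At s = 10% it is 0.35 × 0.90 = 0.315.
- **(B) CRi still a PR at stage 1, rescored at the final analysis.** The stage-1 rule is applied to all responders at 0.35. The final count is the stage-1 responders, each kept with probability 1 − s, plus Bin(16, 0.35 × (1 − s)).

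| s | 0.35 × (1 − s) | Early stop, A | Power, A | Early stop, B | Power, B |
|---|---|---|---|---|---|
| 0 | 0.3500 | 0.0860 | 0.9034 | 0.0860 | 0.9034 |
| 2% | 0.3430 | 0.0932 | 0.8943 | 0.0860 | 0.9005 |
| 5% | 0.3325 | 0.1050 | 0.8792 | 0.0860 | 0.8950 |
| 10% | 0.3150 | 0.1273 | 0.8498 | 0.0860 | 0.8822 |
| 20% | 0.2800 | 0.1830 | 0.7724 | 0.0860 | 0.8379 |

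T-LGL responders dilute s. If half of the responders are CLL/SLL and 10% of those are CRi, then s = 0.5 × 10% = 5%, and power is 0.879 (A) or 0.895 (B).

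**4. Which case applies.** Section 14.2.2 says: "The first response evaluation will be assessed after the first cycle of treatment then at the end of three cycles". A clinical CR first seen after cycle 1 would have its marrow about three months later, at roughly month 4, which is after the cycle-3 evaluation. An eventual CRi may therefore still be a PR at the stage-1 look, which favours B. The document fixes neither the date of that look nor a cut-off for ORR, so A is not excluded.

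**The case against.** The strongest reply is that this is a numbering slip. CRi sits out of order, after three early-death categories and just before the conventional code 9, and a statistician who also read Section 10.2 would probably query the range before applying it. That is plausible, but it is inference. The written rule for the primary analysis still says the opposite, and no other section corrects it.

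The second reply is that the event is uncommon. Under Section 10.2 a patient must meet the CR criteria, including the Group B blood counts, and then have a hypocellular marrow. No CRi rate in the document supports s = 10% or 20%. At s = 2% power is 0.894 (A) or 0.9005 (B), which is immaterial. Pivotal results are also infrequent: at a true ORR of 35%, the chance of passing stage 1 and finishing on exactly 5/26 is 0.027. The chance of exactly 2/10 is 0.176, but that matters only in case A. In either situation one of those few responders must also be a CRi. All of this stands, and it limits the expected size.

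Third, the progression label governs the response-rate analysis only. PFS in Section 10.1 uses objective disease progression and need not change. That stands too.

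Fourth, whether a later CRi replaces an earlier PR depends on a separate gap, since neither best overall response nor an ORR cut-off is defined. That is correct, but if CRi counts as a response the order no longer matters for this point.

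**Conclusion.** The concern holds. Followed literally, Section 14.6.2 scores a CLL/SLL patient with CRi as a treatment failure on the primary endpoint, while the same patient without a marrow is a responder. One such patient can turn 5/26 into 4/26 and, if the marrow result is available in time, 2/10 into 1/10.

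The contradiction rests on no assumption; its numerical size does. If the true ORR of 35% includes CRi, power falls from 0.903 to 0.895 (B) or 0.879 (A) at an assumed CRi share of 5%, and to 0.882 or 0.850 at 10%. Timing makes B the more likely case. There is no effect if no CRi occurs, none on T-LGL patients, and no power loss against plan if the 35% target was meant to exclude CRi. This should be fixed before Phase II responses are scored, but it does not undermine the design.

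**What to change.** Replace the failure-range sentence in Section 14.6.2 with: *Categories 1, 2 and 8 (CR, PR, CRi) are responses; category 3 (SD) is a non-response; categories 4 to 7 and 9 are treatment failures. ORR = CR + CRi + PR.*

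The cost is one sentence. Sample size, boundaries, visits and procedures stay as they are, and the design keeps its power of 0.903, type I error of 0.079 and early-stopping probability of 0.736 at a 10% ORR.
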